Blood oxygen saturation will be measured using a standard pulse oximeter. If possible, the same type of probe should be used for all subjects enrolled at the site while they are hospitalized. The SpO₂ should be measured either in a sitting or supine position after 5 minutes of rest in a quiet environment. Subjects should be encouraged to sit still during the measurements. Pulse oximetry measurements using finger, toe, earlobe or frontal sensors are considered acceptable. If using the digits, nail polish should be removed, and warmth and capillary refill should be assessed, since adequate arterial pulse strength is necessary for obtaining accurate SpO₂ measurements. The sensor should not be placed on sites distal to indwelling arterial catheters, blood pressure cuffs, or venous engorgement (eg, arteriovenous fistulas, blood transfusions). If supplemental oxygen is provided to the subject by either nasal cannula, face mask, or a reservoir system, remove supplemental oxygen while the subject is appropriately monitored. Wait for either 5 minutes to elapse with oxygen saturation maintained at or above 94%, or until saturation declines to less than 94%. (For subjects with known pre-influenza illness SpO₂ levels of <94%, the pre-influenza SpO₂ level should be used as target level instead of 94%). Document those findings, then either return to previous level of supplemental oxygen therapy or discontinue therapy. For subjects receiving invasive or non-invasive mechanical ventilation, peripheral oxygen saturation should be measured with the ventilatory support in place, and it should be recorded that the measurement was with supplemental oxygen.

Blood pressure, pulse rate, and respiratory rate measurements should be preceded by at least 5 minutes of rest in the supine position in a quiet setting without distractions (eg, television, cell phones). These measurements will be assessed with a completely automated device. Manual techniques will be used only if an automated device is not available.

The level of consciousness will be measured according to the ACVPU scale (alert, new confusion, voice, pain, unresponsive).¹⁰

- Alert: The subject is fully awake. This subject will have spontaneously opening of the eyes, will respond to voice, and will have motor function.

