Electrocardiogram data will be summarized by ECG parameter. Descriptive statistics will be calculated at baseline and for observed values and changes from baseline at each scheduled time point. Frequency tabulations of the abnormalities will be made.

The ECG variables that will be analyzed are heart rate, PR interval, QRS interval, QT interval, and QTc interval using the following correction methods: QTcB and QTcF.^{1,5,7,14}

Descriptive statistics of QTc intervals and changes from baseline will be summarized at each scheduled time point. The percentage of subjects with QTc interval >450 milliseconds, >480 milliseconds, or >500 milliseconds will be summarized, as will the percentage of subjects with QTc interval increases from baseline >30 milliseconds or >60 milliseconds.

All clinically relevant abnormalities in ECG waveform that are changes from the baseline readings will be reported (eg, changes in T-wave morphology or the occurrence of U-waves).

The percentage of subjects with abnormalities will be tabulated by treatment arm as received.

Vital Signs

Descriptive statistics of temperature, pulse rate, respiratory rate, blood pressure (systolic and diastolic) (supine) values, oxygen saturation values, and changes from baseline will be summarized at each scheduled time point by treatment group. For oxygen saturation, an overview will be presented for the number of subjects that require supplemental oxygen. The percentage of subjects with values beyond clinically important limits for pulse and systolic and diastolic blood pressure will be summarized ([Attachment 4](#)).

For each subject, the NEWS2 will be derived based on the vital signs data, peripheral blood oxygen saturation, and ACVPU scale ([Attachment 5](#)).^{13,17} The NEWS2 will be summarized by time point and treatment group. Frequency tabulations of the ACVPU score, by time point and treatment group will be provided.

Physical Examination

Descriptive statistics of changes from baseline will be summarized at each scheduled time point.

Physical examination findings will be listed.

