4.1. Demographics and Baseline Characteristics

Demographics and baseline disease characteristics will also be done on the PP and ITT-ni sets.

Descriptive statistics or frequency tabulation will be provided for the following parameters.

- Demographic parameters:
 - Sex (Male, Female)
 - Race (White, Black or African American, Asian, American Indian or Alaska Native, Native Hawaiian or Other Pacific Islander, Multiple). The specification of the category ‘Multiple’ will only be listed. The ‘Not reported category’ will not be added for the denominator.
 - Ethnicity (Hispanic or Latino, Not Hispanic or Latino)
 - Country
 - Geographic region (Based on country according to UN classification of Geographic regions^[9]: Europe/Africa, Northern-America, Latin America and the Caribbean, Asia and Oceania)
 - Age (years and categories: 13-17 years [≥ 13 - < 18], 18-65 years [≥ 18 - ≤ 65], 66-85 years [> 65 - ≤ 85])
 - Age (years and categories: Adolescents (12-17 years) [≥ 12 - ≤ 17], Adults (18-64 years) [≥ 18 - ≤ 64], From 65 to 84 years [≥ 65 - ≤ 84], 85 years and over [≥ 85])
 - Weight at baseline (kg)
 - Height at baseline (cm)
 - BMI at baseline = Weight at baseline (kg) / (Height at baseline (m))² (rounded to 1 decimal. Although available in the raw data, BMI will be recalculated from last weight and height measurement before start of treatment)
 - Current Tobacco use: tobacco, cigarettes, cigars, patches/gum, pipes, E-cigarettes or equivalent, smokeless tobacco (Yes, No, Missing). Note that ‘No’ also includes ex-smokers.
 - Childbearing potential (only listed)

- Baseline disease characteristics:
 - Influenza A subtype category (A/H1N1, A/H3N2, No subtype)
 - Baseline influenza A viral load (\log_{10} vp/mL), assessed by qRT-PCR
 - Baseline influenza A viral titer (\log_{10} TCID₅₀/mL) assessed by viral culture

- qRT-PCR negativity at baseline
- Viral culture negativity at baseline
- Broad respiratory panel (show the reported pathogen)
- Return to daily activities at baseline
- Patient Global Impression of Severity of Influenza symptoms at baseline
- EQ-5D VAS at baseline
- EQ-5D Valuation index at baseline
- NEW2 Score at screening (4-5, ≥ 6), as randomized
- NEW2 Score at screening (4-5, ≥ 6), actual
- Hospital recovery scale category at baseline
- Fundamental hospital recovery scale category at baseline
- Respiration rate at baseline (breaths/min)
- Arterial oxygen saturation at baseline on room air (%)

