7.3. Vital signs

7.3.1. Definitions

Vital signs (including temperature, pulse rate, respiratory rate, and blood pressure), peripheral capillary oxygen saturation, and level of consciousness (AVPU) will be included in the analysis.

Vital Signs abnormalities will be determined according to the WHO grading scale boundaries defined in [Attachment 3, Table 4: Resolution Criteria for Vital Signs](#).

Worst abnormalities are determined over the whole observational period and per phase (treatment, follow-up and combination treatment + follow-up) and per subperiod (treatment, treatment extension), including all post-baseline scheduled and unscheduled measurements.

An abnormality (based on normal ranges) will be considered treatment-emergent if it is worse than the baseline abnormality. If the baseline abnormality is missing, the abnormality is always considered as treatment-emergent. A shift from “abnormally low” at baseline to “abnormally high” post-baseline (or vice versa) is also treatment-emergent.

Assessments (except oxygen saturation) taken while the subject was not in a supine position will not be included in descriptive statistics but will be considered in determining worst case values.

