7.3.2. Analysis Methods

Actual values and changes from baseline will be summarized by treatment group at each scheduled timepoint.

A tabulation of the abnormalities per timepoint will be presented. This table will also show the number and percentage of subjects per abnormality, the number and percentage of subjects per treatment-emergent abnormality, and the cumulative number of subjects per treatment-emergent abnormality per post-baseline timepoint. Include in this table the safety follow-up visit, the Day 28 final study visit and the last study visit.

Additionally, a tabulation of the worst abnormality will be presented. This table will show the number and percentage of subjects per worst abnormality.

A cross-tabulation of the worst abnormality versus baseline will be presented per phase (treatment, follow-up and combination treatment + follow-up) and per subperiod (treatment, treatment extension). This table will also show the number and percentage of subjects per worst abnormality, the number and percentage of subjects per treatment-emergent worst abnormality, and the cumulative number of subjects per treatment-emergent abnormality.

Mean \pm SE graphs over time for the actual values and changes from baseline will be generated for all tests performed.

Vital signs data for subjects having at least one treatment-emergent abnormality will be listed.

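### Post-baseline SpO2 summaries, grades and treatment-emergent flags do not separate room-air from supported readings, so 95% or more on a ventilator counts as Normal and coming off support can be flagged as a new abnormality

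*Protocol*

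**What the plan says.** **How SpO2 is measured (protocol 9.6.4).** The conditions depend on the subject's support.

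- Ventilated: "For subjects receiving invasive or non-invasive mechanical ventilation, peripheral oxygen saturation should be measured with the ventilatory support in place". The reading is then recorded as taken with supplemental oxygen.
- Cannula, mask or reservoir oxygen: the oxygen is removed under monitoring, and the instruction is "Wait for either 5 minutes to elapse with oxygen saturation maintained at or above 94%, or until saturation declines to less than 94" percent. Subjects with a known pre-influenza level below 94% use that level as the target instead.

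**How SpO2 is analysed.** Protocol 11.11 plans that "oxygen saturation values, and changes from baseline will be summarized at each scheduled time point by treatment group". SAP 7.3.2 says the same of all vital signs: "Actual values and changes from baseline will be summarized by treatment group at each scheduled timepoint". SAP Attachment 3 grades saturation as Normal (95-100%), Grade 1 (90 to below 95%), Grade 2 (85 to below 90%) and Grade 3 (below 85%), with no reference to support. SAP 7.3.1 adds: "An abnormality (based on normal ranges) will be considered treatment-emergent if it is worse than the baseline abnormality". A missing baseline makes any later abnormality treatment-emergent. Baseline (SAP 2.5) is the last pre-dose assessment, on or off support. The only exception in SAP 7.3.1 that names saturation concerns body position.

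**Where support is taken into account.**

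- Protocol 11.11 continues: "For oxygen saturation, an overview will be presented for the number of subjects that require supplemental oxygen".
- SAP 4.1 lists "Arterial oxygen saturation at baseline on room air" as a baseline row of its own.
- SAP 4.6 tabulates oxygen supplementation by visit, and SAP 5.3.1.1 tabulates type of support and ventilation started after baseline.
- For subjects on invasive ventilation, SAP 7.6.1 discards the observed saturation and substitutes 90% in NEWS, or 82% for those scored on NEWS2 SpO2 scale 2.

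**The concern.** SpO2 is a named safety measure. A change from baseline, or a shift in grade, is interpretable only if both readings were taken under comparable conditions. Here one subject's two readings may be on a ventilator and on room air, and nothing in SAP 7.3 tells the programmer to distinguish them.

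Two errors become possible in the per-time-point, change and shift tables. A subject who worsens and is intubated can move to a better saturation grade. A subject who recovers and comes off the ventilator can acquire a treatment-emergent abnormality. A safety reader working from those tables alone could not tell which Normal readings were obtained on a ventilator, because the oxygen and ventilation tabulations elsewhere are not linked to saturation values.

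**Working it through.** The plan states no figure for this point, so there is none to reproduce. The check applies the written rules to readings that protocol 9.6.4 can generate.

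**Step 1: grades under Attachment 3.** 100, 98 and 95% are Normal; 94, 93, 92 and 90% are Grade 1; 89 and 85% are Grade 2; 84 and 82% are Grade 3. The same underlying state can land in three places. A room-air value of 88% is Grade 2. An oxygen user whose test ends at 93% is Grade 1. A ventilated 97% is Normal.

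**Step 2: the treatment-emergent rule (flag if the grade is worse than the baseline grade).**

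| Baseline reading | Later reading | Change (points) | Grades | Flag |
|---|---|---|---|---|
| 97%, ventilated | 93%, room air | -4 | Normal to 1 | Yes |
| 94%, ventilated | 93%, room air | -1 | 1 to 1 | No |
| 93%, room air | 93%, after a later extubation | 0 | 1 to 1 | No |
| 88%, room air | 97%, ventilated | +9 | 2 to Normal | No |

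The first row is a recovery shown as a new abnormality. The last is a deterioration shown as a gain. The middle rows mark the limits. The false flag needs a supported baseline of 95% or more, which in practice means a subject ventilated at baseline. Inclusion criterion 5 admits non-ventilated subjects below 94% on room air, or at least 3% below a known low pre-influenza level. If their last pre-dose reading is similar, they are already Grade 1 or worse.

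**Step 3: size.** False flags in an arm of n subjects equal

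n × (share ventilated at baseline) × (share of those reading 95% or more) × (share of those later reading 90-94% off support).

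The documents give none of the three shares. The nearest figure is the sample-size assumption (protocol 11.3) of 5% of placebo subjects on invasive ventilation at Day 6: 0.05 × 300 = 15. Under the planning common odds ratio of 1 - 0.38 = 0.62, the cumulative odds of being in a given category or better are divided by 0.62:

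- Category 4 or better: 0.90/0.10 = 9; 9/0.62 = 14.52; probability 0.9356.
- Category 5 or better: 0.95/0.05 = 19; 19/0.62 = 30.65; probability 0.9684.
- Category 5: 0.9684 - 0.9356 = 0.0328, or 9.9 of 300 on pimodivir.

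These inputs agree with the plan. The Whitehead formula with two-sided 5% alpha and 90% power gives a total of 601.4 against the stated 600.

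So about 15 and 10 subjects per arm would contribute ventilated readings at Day 6 if the planning assumptions held. That is a scale for readings affected on one day. It is not a count of false flags, which depends on baseline status, and it omits non-invasive ventilation, for which no share is given.

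**The case against.** The case for leaving the plan alone has real content.

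- **Support is not ignored.** The displays listed above show who was on oxygen or a ventilator. Invasive ventilation is category 5 of the primary scale, and respiratory failure is an adjudicated complication. Deterioration to ventilation cannot disappear from the report. This stands, and it confines the problem to the saturation tables.
- **The worst-abnormality table is largely protected.** It uses all post-baseline scheduled and unscheduled readings, and inpatients are measured three times daily. A post-baseline 88% stays Grade 2 after a later 97% on the ventilator. This stands, except for a subject whose post-baseline readings are all supported and 95% or more.
- **Oxygen users are not all recorded near 93%.** Those who hold their saturation are recorded at 94% or above, and some have their own target. Protocol 9.6.4 asks for the findings to be documented without saying that the first value below 94% is the one kept. Extra routine measurements are entered too. This stands: truncation just below 94% is possible, not general.
- **Protocol 11.11 does not grade saturation.** It limits out-of-range percentages to pulse and blood pressure. This is correct; grading and flags come from SAP 7.3.1 and Attachment 3.
- **Table layouts sit in separate mock shells.** They may split the displays, but a split layout would not change the SAP's written flag rule.

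A reader might go further and infer that the tables run the wrong way overall, so that a drug that frees subjects from support sooner would show more saturation abnormalities. The documents do not support that. The two artefacts can act in opposite directions between arms, and any net excess would have to be assumed.

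**Conclusion.** The point holds in limited form. Post-baseline SpO2 values, changes, grades and treatment-emergent flags combine readings taken under different support, and no rule separates them. A supported 95% or more counts as Normal. A subject ventilated at baseline at 95% or more who comes off support to 90-94% is wrongly flagged. It would be too strong to say that intubated subjects always count as Normal or that extubated subjects always become new abnormalities: 90-94% on a ventilator is Grade 1, and 93% after a Grade 1 baseline is not flagged.

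The consequence is confined to descriptive safety tables. No hypothesis test on SpO2 is planned, and the primary endpoint and sample size are unaffected. No arm-specific magnitude can be derived. The conclusion assumes that sites follow protocol 9.6.4 and that the tables are programmed as SAP 7.3 reads. It is worth correcting because the SAP already rejects observed saturation on invasive ventilation when scoring NEWS and NEWS2 scale 2, so SAP 7.3 is inconsistent with SAP 7.6.1.

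**What to change.** Amend SAP 7.3 as follows.

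1. Present SpO2 values, changes from baseline and grades by support status at the time of the reading: room air, supplemental oxygen, non-invasive ventilation, invasive ventilation.
2. Grade only room-air readings. Show supported readings as their own categories in the per-time-point, worst-value and shift tables, so that a ventilated reading never appears as Normal. For invasive ventilation, an alternative is the SAP 7.6.1 substitution: 90% is Grade 1 and 82% is Grade 3, and a later 93% is not flagged against either. It does not cover non-invasive ventilation.
3. Assign the treatment-emergent flag only when the baseline and later readings share the same support status. Put subjects whose baseline was on support in a separate shift row, and exempt them from the missing-baseline rule. Otherwise leaving their baseline ungraded would make every later abnormality treatment-emergent.
4. Footnote that readings after oxygen removal may stop just below 94%, or below the subject's own pre-influenza level, under protocol 9.6.4. Splitting by support does not remove that effect.

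The cost is SAP wording and programming. The room-air indicator is already used in SAP 7.6.1 and Attachment 6, and support type is collected on the oxygen supplementation form (SAP 5.3.1.1). The drawbacks are smaller numbers per cell and room-air means that describe only subjects off support, a group selected after randomisation. The tables should say so.

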11.12. Interim Analysis

All interim analyses will be performed by an independent Statistical Support Group (SSG) and will be reviewed by the Independent Data Monitoring Committee (IDMC; see Section 11.13). Only the IDMC and the SSG will be unblinded to the data. The IDMC will provide recommendations to a Sponsor Committee.

An interim analysis will be implemented to assess lack of efficacy in the subgroup with time since onset of influenza symptoms between 72 and 96 hours.

- In case lack of efficacy is concluded for the subgroup with time since onset of influenza symptoms between 72 and 96 hours:
 - Enrollment in this subgroup will be stopped
 - Sample size re-estimation will be performed based on the subgroup with time since onset of influenza symptoms ≤ 72 hours and consequently, the sample size of this subgroup may be increased. The maximum number of subjects that may be enrolled in this subgroup will be approximately 900.
 - Futility will be assessed in the subgroup with time since onset of influenza symptoms ≤ 72 hours based on re-estimated sample size.
 - At the final analysis, hypotheses will be evaluated in the subgroup with time since onset of influenza symptoms ≤ 72 hours.
- In case no lack of efficacy is concluded for the subgroup with time since onset of influenza symptoms between 72 and 96 hours:
 - The subgroup with time since onset of influenza symptoms between 72 and 96 hours will be continued in the study.
 - Sample size re-estimation will be performed based on all subjects. The sample size may be increased. The maximum total number of subjects that may be enrolled in the study will be approximately 900. The study population should consist of at least 75% of subjects with first administration of study drug ≤ 72 hours since onset of influenza symptoms.
 - Futility will be assessed in all subjects based on re-estimated sample size.
 - At the final analysis, hypotheses will be evaluated in all subjects.

Details on the statistical decision rules will be provided in a separate Modeling and Simulation Report. The interim analysis will be conducted at the end of the first influenza season when between 300 and 450 subjects have been enrolled or during the season when 450 subjects have been enrolled. Further details will be specified in the IDMC charter.

11.13. Independent Data Monitoring Committee

An IDMC will be established to monitor data on a regular basis. The committee will meet periodically to review interim data. After the review, the IDMC will make recommendations regarding the continuation of the study. The details will be provided in a separate IDMC charter.

The IDMC will consist of at least 3 members, including one medical expert in the relevant therapeutic area and at least one statistician knowledgeable about statistical methods for clinical studies and sequential analysis of study data. One of these individuals will chair the Committee. The IDMC responsibilities, authorities, and procedures will be documented in its charter.

11.14. Adjudication Committee

A blinded Adjudication Committee (AC) will be established to adjudicate AEs as complications based on predefined criteria (pulmonary versus extrapulmonary, major versus minor, as well as infectious versus noninfectious complications). The AC will receive data on AEs, including medical assessments (eg, chest X-ray results, lab results) and concomitant therapy of cases selected from the AEs. Details will be provided in an AC charter.

12. ADVERSE EVENT REPORTING

Timely, accurate, and complete reporting and analysis of safety information from clinical studies are crucial for the protection of subjects, investigators, and the sponsor, and are mandated by regulatory agencies worldwide. The sponsor has established Standard Operating Procedures in conformity with regulatory requirements worldwide to ensure appropriate reporting of safety information; all clinical studies conducted by the sponsor or its affiliates will be conducted in accordance with those procedures.

12.1. Definitions

12.1.1. Adverse Event Definitions and Classifications

Adverse Event

An AE is any untoward medical occurrence in a clinical study subject administered a medicinal (investigational or non-investigational) product. An AE does not necessarily have a causal relationship with the treatment. An AE can therefore be any unfavorable and unintended sign (including an abnormal finding), symptom, or disease temporally associated with the use of a medicinal (investigational or non-investigational) product, whether or not related to that medicinal (investigational or non-investigational) product (definition per International Conference on Harmonisation [ICH]).

This includes any occurrence that is new in onset or aggravated in severity or frequency from the baseline condition, or abnormal results of diagnostic procedures, including laboratory test abnormalities.

Note: The sponsor collects AEs starting with the signing of the ICF/assent form (refer to Section 12.3.1, All Adverse Events, for time of last AE recording).

Serious Adverse Event

An SAE based on ICH and European Union Guidelines on Pharmacovigilance for Medicinal Products for Human Use is any untoward medical occurrence that at any dose:

- Results in death.
- Is life-threatening
(The subject was at risk of death at the time of the event. It does not refer to an event that hypothetically might have caused death if it were more severe.).
- Requires inpatient hospitalization or prolongation of existing hospitalization.
- Results in persistent or significant disability/incapacity.
- Is a congenital anomaly/birth defect.
- Is a suspected transmission of any infectious agent via a medicinal product.
- Is Medically Important*.

*Medical and scientific judgment should be exercised in deciding whether expedited reporting is also appropriate in other situations, such as important medical events that may not be immediately life threatening or result in death or hospitalization but may jeopardize the subject or may require intervention to prevent one of the other outcomes listed in the definition above. These should usually be considered serious.

If a serious and unexpected AE occurs for which there is evidence suggesting a causal relationship between the study drug and the event (eg, death from anaphylaxis), the event must be reported as a serious and unexpected suspected adverse reaction even if it is a component of the study endpoint (eg, all-cause mortality).

Unlisted (Unexpected) Adverse Event/Reference Safety Information

An AE is considered unlisted if the nature or severity is not consistent with the applicable product reference safety information. For pimodivir, since no serious ADRs are currently identified in the IB, all related SAEs are considered unexpected for reporting purposes. For medications part of the SOC treatment, the expectedness of an AE will be determined by whether or not it is listed in the manufacturer's prescribing information.

Adverse Event Associated With the Use of the Drug

An AE is considered associated with the use of the drug if the attribution is possible, probable, or very likely by the definitions listed in Section 12.1.2, Attribution Definitions.

